### 7.1.3 Methotrexate

MTX is a folic acid reductase inhibitor used as a disease-modifying, anti-rheumatic drug for the treatment of autoimmune diseases.

Adverse events (AEs) that may be experienced by subjects treated with MTX include:

- Gastrointestinal: nausea, vomiting, diarrhea, stomatitis
- Hematologic and oncologic: leukopenia, thrombocytopenia
- Hepatic: hepatotoxicity, increased serum alkaline phosphatase, increased serum bilirubin, increased serum transaminases
- Infection: increased susceptibility to infection
- General: malaise, fatigue, dizziness, alopecia, photosensitivity

Additionally, MTX can cause fetal death or teratogenic effects. Pregnancy should be avoided if either partner is receiving MTX, during, and for a minimum of three months after MTX therapy for the non-vasectomized male. For females of child bearing potential, pregnancy should be avoided for at least one ovulatory cycle after MTX therapy. Refer to the current version of the FDA-approved MTX Full Prescribing Information for detailed information concerning the safety profile of MTX.

### 7.2 Rationale for this Study

Immunogenicity (anti-pegloticase antibodies) in response to pegloticase therapy may lead to loss of therapeutic response and/or AEs, including IRs. IRs occurred more commonly in subjects whose sUA values increased above 6 mg/dL after initially showing response following the first 1 or 2 infusions. In the Phase 3 program, the titer of the anti-drug antibody was also associated with loss of response, with subjects having the highest levels of anti-drug antibodies showing the lowest response rates.

The development of anti-drug antibodies can be influenced by drug and treatment-related factors. as well as patient characteristics. A potential prophylactic strategy to manage anti-drug antibody response with pegloticase is the co-administration of immunomodulating therapy. Various methods are used to reduce antibody production, the most common of which is the use of traditional rheumatoid arthritis disease-modifying drugs, such as MTX, azathioprine, mycophenolate mofetil, leflunomide, and others, as is commonly implemented with rheumatoid arthritis biological therapy (e.g., infliximab and other infusible and subcutaneous antibody products) [Strand et al, 2017].

MTX is the most commonly used non-biological disease modifying agent worldwide and is frequently used in combination with other biological therapies [Strand et al, 2017].

In the current study, MTX will be evaluated for its ability to reduce antidrug antibodies against pegloticase that lead to loss of response and that are associated with IRs, thereby allowing patients to receive a longer course of therapy or repeated courses of therapy, as needed.

#### 7.3 Rationale for Dose Selection

The dose and dose regimens used in this study are those specified by the prescribing information for pegloticase and MTX, respectively.

#### STUDY OBJECTIVES

The overall objective of the study is to assess the efficacy, safety, tolerability, and pharmacokinetics (PK) of the concomitant use of MTX with pegloticase to enhance the response rate seen with pegloticase alone in adults with uncontrolled gout.

# Primary Objective

The primary objective is to estimate the response rate during Month 6 (Weeks 20, 22, and 24), as measured by the sustained normalization of serum uric acid (sUA) to <6 mg/dL for at least 80% of the time during Month 6 in subjects receiving pegloticase with MTX.

### Secondary Objectives

- Estimate the response rate during Month 3 (Weeks 10, 12 and 14), as measured by the sustained normalization of sUA to <6 mg/dL for at least 80% of the time during Month 3 in subjects receiving pegloticase with MTX.
- Estimate the overall response rate, as measured by the sustained normalization of sUA to <6 mg/dL for at least 80% of the time during Month 3 (Weeks 10, 12 and 14) and Month 6 (Weeks 20, 22 and 24) combined in subjects receiving pegloticase with MTX.
- Estimate the 5 mg/dL response rate during Month 3, during Month 6, and Overall (Months 3 and 6 combined), as measured by the sustained normalization of sUA to <5 mg/dL for at least 80% of the time in subjects receiving pegloticase with MTX.

KRYSTEXXA IND: 010122

Version 3.0, Adminstrative Change 1

• Estimate the mean change from baseline to Weeks 14, 24, 36, and 52 in sUA in subjects receiving pegloticase with MTX.

# **Exploratory Objectives**

- Estimate the response rate during Month 9 (Weeks 32, 34 and 36), as measured by the sustained normalization of sUA to <6 mg/dL for at least 80% of the time during Month 9 in subjects receiving pegloticase with MTX.
- Estimate the response rate during Month 12 (Weeks 48, 50 and 52), as measured by the sustained normalization of sUA to <6 mg/dL for at least 80% of the time during Month 12 in subjects receiving pegloticase with MTX.
- Estimate the 5 mg/dL response rate during Month 9 (Weeks 32, 34 and 36), as measured by the sustained normalization of sUA to <5 mg/dL for at least 80% of the time during Month 9 in subjects receiving pegloticase with MTX.
- Estimate the 5 mg/dL response rate during Month 12 (Weeks 48, 50 and 52), as measured by the sustained normalization of sUA to <5 mg/dL for at least 80% of the time during Month 12 in subjects receiving pegloticase with MTX.
- Estimate the time to first sUA >6 mg/dL in subjects receiving pegloticase with MTX.
- Estimate the time to two consecutive sUAs >6 mg/dL (stopping rule) in subjects receiving pegloticase with MTX.
- Estimate the mean change from baseline to Week 24, 36 and 52 in urate volume and gout erosions using DECT scan of the hands and feet in subjects receiving pegloticase with MTX.
- Estimate the mean change from baseline in number of joints affected by tophi in subjects receiving pegloticase with MTX.
- Estimate the mean change from baseline to Weeks 14, 24, 36, and 52 in tender joint count (68 point scale) in subjects receiving pegloticase with MTX.
- Estimate the mean change from baseline to Weeks 14, 24, 36, and 52 in swollen joint count (66 point scale) in subjects receiving pegloticase with MTX.
- Estimate the mean change from baseline to Weeks 14, 24, 36, and 52 in the Health Assessment Questionnaire – Disability Index (HAQ-DI) in subjects receiving pegloticase with MTX.
- Estimate the mean change from baseline to Weeks 14, 24, 36, and 52 in the HAQ pain score in subjects receiving pegloticase with MTX.
- Estimate the mean change from baseline to Weeks 14, 24, 36, and 52 in the HAQ health score in subjects receiving pegloticase with MTX.
- Estimate the mean change from baseline to Weeks 14, 24, 36, and 52 in patient global assessment of gout in subjects receiving pegloticase with MTX.
- Estimate the mean change from baseline to Weeks 14, 24, 36, and 52 in physician global assessment of gout in subjects receiving pegloticase with MTX.

 Estimate the mean change from baseline to Weeks 14, 24, 36, and 52 in subject assessment of average, least, and worst joint pain in subjects receiving pegloticase with MTX.

- Estimate the proportion of subjects achieving 20%, 50%, or 70% improvement based on gout chronic response criteria at Weeks 14, 24, 36, and 52 in subjects receiving pegloticase with MTX.
- Assess the PK of pegloticase in subjects receiving concomitant MTX.
- Assess the incidence of anti-PEG and anti-Uricase IgG antibodies.

### Safety and Tolerability Objectives

Assess the incidence of infusion reactions (IRs), anaphylaxis, gout flares, cardiovascular
events, and the adverse event (AE/SAE) profile overall and potentially attributed to the
combination of pegloticase and MTX.

#### 9 INVESTIGATIONAL PLAN

# 9.1 Overall Study Design and Plan

This study is a multicenter, open-label, efficacy and safety study of pegloticase in combination with MTX in adult subjects with uncontrolled gout.

The study design will include: 1) up to a 2-week Screening Period (screening should be complete within 2 weeks prior to Week -4), 2) a 4-week MTX Run-in Period (Week – 4 through Day 1); 3) a 52-week Pegloticase + IMM (Pegloticase + MTX) Period 4) a Safety Follow-up (Phone/Email/Site Visit) and 5) a 3 and 6 month Post Treatment Follow-up.

All subjects who meet eligibility criteria at Screening will begin oral MTX at a dose of 15 mg weekly for 4 weeks prior to the first dose of pegloticase.

Subjects will also take folic acid 1 mg orally every day beginning at Week -4 (the start of MTX) and continuing until prior to the Week 52 Visit. Subjects must be able to tolerate MTX at a dose of 15 mg during the MTX Run-in (Week -4 through Day 1) to be eligible to participate in the Pegloticase + IMM Period. Subjects who are unable to tolerate MTX at a dose of 15 mg during the MTX Run-in Period will be considered screen failures.

Subjects who take at least one dose of MTX and who are females of childbearing potential, will receive a safety follow-up Phone Call/E-mail/Site Visit approximately 30 days after the last dose of MTX to verify at least one ovulatory cycle has occurred after the last dose of MTX. If the subject has not ovulated, a urine pregnancy test will be performed. Subjects who receive at least one dose of MTX and who are non-vasectomized males, will be asked, 3 months after MTX discontinuation, regarding partner pregnancy.

Protocol: HZNP-KRY-201 Version 3.0, Adminstrative Change 1

KRYSTEXXA IND: 010122

All subjects who complete the Run-In Period will receive the first pegloticase infusion on Day 1. All subsequent doses and study visits will be scheduled based on the Day 1 visit date.

It is required that before a subject begins the Pegloticase + IMM Period, he or she has been taking at least one protocol standard gout flare prophylaxis regimen (i.e. colchicine and/or non-steroidal anti-inflammatory drugs and/or low-dose prednisone  $\leq 10$  mg/day) for  $\geq 1$  week before the first dose of pegloticase and continues flare prophylaxis per American College of Rheumatology guidelines [Khanna D et al.2012] for the greater of 1) 6 months, 2) 3 months after achieving target serum urate (sUA < 6 mg/dL) for patients with no tophi detected on physical exam, or 3) 6 months after achieving target serum urate (sUA < 5 mg/dL) for patients with one or more tophi detected on initial physical exam that have since resolved. For IR prophylaxis, fexofenadine (60 mg or 180 mg orally based on the Principal Investigator's discretion) will be taken the day before each infusion; fexofenadine (60 mg or 180 mg orally based on the Principal Investigator's discretion) and acetaminophen (1000 mg orally) will be taken the morning of each infusion; and methylprednisolone (125 mg IV) given over the infusion duration 10-30 minutes (recommended) or hydrocortisone (200 mg IV) will be administered immediately prior to each infusion.

During the Pegloticase + IMM Period, pegloticase 8 mg will be administered intravenously (IV) every 2 weeks from Day 1 through the Week 50 Visit for a total of 26 infusions; pegloticase will be administered after all pre-dose study visit assessments have been completed at each visit. The date and start and stop time of infusion will be recorded. Serum uric acid stopping rules will be applied: subjects with sUA level >6 mg/dL at 2 consecutive study visits beginning with the Week 2 Visit will discontinue treatment, complete the End of Pegloticase Infusion Visit procedures within 2 weeks and continue the subject visits according to the protocol (without treatment).

During the Pegloticase + IMM Period, subjects will be instructed to take MTX weekly on the same day each week, within 1 to 3 days prior to each pegloticase infusion and one additional weekly dose after the last infusion for subjects who have not stopped pegloticase due to sUA stopping rules; however, if a subject does not do so, MTX must be taken ≥60 minutes prior to each pegloticase infusion.

After Day 1, if a subject becomes unable to tolerate 15 mg of MTX, the MTX dose may be reduced and/or discontinued, and the subject may remain in the study (see Section 9.4.6.3.2.2).

The Investigator will review the clinical status and individual subject treatment goals at Week 24, and the End of Pegloticase Infusions Visit (if applicable) and the Week 52/End of study/Early Termination Visit.

Serum samples for measurement of sUA levels will be collected at the Screening Visit, the Week -4 Visit (prior to the first dose of MTX), and the Week -2 Visit during the MTX Run-in Period; within 48 hours prior to each pegloticase infusion and after the end of each pegloticase infusion prior to discharge from the site during the Pegloticase + IMM Period; at the non-infusion Week 52/End of Study/Early Termination Visits and at the Post Treatment 3 and 6 Month Follow-up Visits. Additional serum samples for sUA levels will be collected at optional non-PRIVATE AND CONFIDENTIAL INFORMATION OF HORIZON THERAPEUTICS IRELAND DAC Page 45 of 129

Protocol: HZNP-KRY-201

KRYSTEXXA IND: 010122

Version 3.0, Adminstrative Change 1

infusion (Frequent Sampling) Visits at Weeks 1 and 7. If applicable an sUA sample will need to be collected at the End of Pegloticase Visit if a subject does not continue treatment. Subjects with sUA level >6 mg/dL at 2 consecutive visits beginning at Week 2 visit will discontinue treatment, complete the End of Pegloticase Infusion Visit procedures within 2 weeks and continue the subject visits according to the protocol (without treatment).

[figure not shown]
Samples for measurement of sUA levels, PK analysis of pegloticase, pegloticase immunogenicity and MTX Polyglutamate analysis will be collected at visits indicated in the Schedule of Assessments (Section 2.1).

Safety assessments, including monitoring and recording of all AEs, whether or not drug-related, measurement of vital signs, physical examinations, and monitoring of hematology and blood chemistry, will be performed.

The total blood volume to be collected from each subject during this study is approximately 700 mL, increased to 750 mL for the subjects participating in the optional visits at Week 1 and Week 7.

An overview of the study design is presented in the schematic below, and details of study activities are provided in Section 9.1.

Figure 9.1 Schematic of Study Design

## 9.2 Discussion of Study Design

This study is a multicenter, open-label, efficacy and safety study of pegloticase in combination with MTX in adult subjects with uncontrolled gout.

Immunogenicity (anti-pegloticase antibodies) in response to pegloticase therapy may lead to loss of therapeutic response and/or AEs, including IRs. A potential prophylactic strategy to manage anti-drug antibody response with pegloticase is the co-administration of immunomodulating therapy. MTX is the most commonly used non-biological disease modifying agent worldwide and is frequently used in combination with other biological therapies [Strand et al, 2017].

The study design will include: 1) up to a 2-week Screening Period (screening should be complete within 2 weeks prior to Week -4), 2) a 4-week MTX Run-in Period; 3) an End of Pegloticase Treatment Visit if applicable 4) a 52-week Pegloticase + IMM (Pegloticase + MTX) Period 5) a Safety Follow-up (Phone/Email/Site Visit) and 6) a 3 and 6 month Post Treatment Follow-up.

### 9.3 Selection of Study Population

#### 9.3.1 Inclusion Criteria

Eligible subjects must meet all of the following criteria:

1. Willing and able to give informed consent.

KRYSTEXXA IND: 010122 Protocol: HZNP-KRY-201 Version 3.0, Adminstrative Change 1

2. Willing and able to comply with the prescribed treatment protocol and evaluations for the duration of the study.

- 3. Adult men or women  $\geq$ 18 to  $\leq$ 65 years of age.
- 4. Women of childbearing potential (including those with an onset of menopause <2 years prior to screening, non-therapy-induced amenorrhea for <12 months prior to screening, or not surgically sterile [absence of ovaries and/or uterus]) must have negative serum/urine pregnancy tests during the Screening/MTX Run-in Period; subjects must agree to use 2 reliable forms of contraception during the study, one of which is recommended to be hormonal, such as an oral contraceptive. Hormonal contraception must be started ≥1 full cycle prior to Week -4 (start of MTX dosing) and continue for 30 days after the last dose of pegloticase or at least one ovulatory cycle after the last dose of MTX (whichever is the longest duration after the last dose of pegloticase or MTX). Highly effective contraceptive methods (with a failure rate <1% per year), when used consistently and correctly, include implants, injectables, combined oral contraceptives, some intrauterine devices, sexual abstinence, or vasectomized partner.
- 5. Men who are not vasectomized must not impregnate their female partner during the study and for at least 3 months after the last dose of MTX.
- 6. Hyperuricemia at the Screening, Week -4, or Week -2 Visit of the Screening/MTX Run-in Period, as documented by sUA ≥6 mg/dL.
- 7. Uncontrolled gout, defined as meeting the following criteria:
  - sUA ≥6 mg/dL prior to entry into the Pegloticase + IMM Period (any laboratory tests during screening up to and including during the MTX Run-in Period) and at least 1 of the following:
    - inability to maintain sUA <6 mg/dL on other urate-lowering therapy
    - intolerable side effects associated with current urate-lowering therapy
    - functionally limiting tophaceous deposits (including those detected clinically or by DECT imaging)
- 8. Able to tolerate MTX 15 mg for 4 weeks during the Screening/MTX Run-in Period prior to the first dose of pegloticase.

# 9.3.2 Exclusion Criteria

Subjects will be ineligible for study participation if they meet any of the following criteria:

- 1. Weight >160 kg (352 pounds).
- Any serious acute bacterial infection, unless treated and completely resolved with antibiotics at least 2 weeks prior to the Week -4 Visit of the Screening/MTX Run-in Period.
- 3. Severe chronic or recurrent bacterial infections, such as recurrent pneumonia or chronic bronchiectasis.

Protocol: HZNP-KRY-201

KRYSTEXXA IND: 010122

Version 3.0, Adminstrative Change 1

4. Current immunocompromised condition, including current or chronic treatment with systemic immunosuppressive agents, including prednisone >10 mg/day or equivalent dose of other corticosteroid.

- 5. History of any transplant surgery requiring maintenance immunosuppressive therapy.
- 6. Known history of hepatitis B virus surface antigen positivity or hepatitis B DNA positivity.
- 7. Known history of hepatitis C virus RNA positivity.
- 8. Known history of Human Immunodeficiency Virus (HIV) positivity (tested at Screening Visit).
- 9. Glucose -6-phosphage dehydrogenase (G6PD) deficiency (tested at the Screening Visit).
- 10. Severe chronic renal impairment (glomerular filtration rate <25 mL/min/1.73 m^2) or currently on dialysis.
- 11. Non-compensated congestive heart failure or hospitalization for congestive heart failure within 3 months of the Screening Visit, uncontrolled arrhythmia, treatment for acute coronary syndrome (myocardial infarction or unstable angina), or uncontrolled blood pressure (>160/100 mmHg) at the end of the Screening/MTX Run-in Period.
- 12. Pregnant, planning to become pregnant, breastfeeding, planning to impregnate female partner, or not on an effective form of birth control, as determined by the Investigator.
- 13. Prior treatment with pegloticase (KRYSTEXXA), another recombinant uricase (rasburicase), or concomitant therapy with a polyethylene glycol-conjugated drug.
- 14. Known allergy to pegylated products or history of anaphylactic reaction to a recombinant protein or porcine product.
- 15. Contraindication to MTX treatment or MTX treatment considered inappropriate.
- 16. Known intolerance to MTX.
- 17. Receipt of an investigational drug within 4 weeks or 5 half-lives, whichever is longer, prior to MTX administration at Week -4 or plans to take an investigational drug during the study.
- 18. Current liver disease, as determined by alanine transaminase or aspartate transaminase levels >3 times upper limit of normal at the Screening Visit.
- 19. Currently receiving systemic or radiologic treatment for ongoing cancer, excluding non-melanoma skin cancer.
- 20. History of malignancy within 5 years other than non-melanoma skin cancer or in situ carcinoma of cervix.
- 21. Uncontrolled hyperglycemia with a plasma glucose value >240 mg/dL at screening that is not subsequently controlled by the end of the Screening/MTX Run-in Period.
- 22. Diagnosis of osteomyelitis.

KRYSTEXXA IND: 010122 Protocol: HZNP-KRY-201 Version 3.0, Adminstrative Change 1

23. Known history of hypoxanthine-guanine phosphoribosyl-transferase deficiency, such as Lesch-Nyhan and Kelley-Seegmiller syndrome.

- 24. Unsuitable candidate for the study, based on the opinion of the Investigator (e.g., cognitive impairment), such that participation might create undue risk to the subject or interfere with the subject's ability to comply with the protocol requirements or complete the study.
- 25. Alcohol use in excess of 3 alcoholic beverages per week.
- 26. Currently receiving allopurinol and unable to discontinue medication 7 days prior to MTX dosing at Week -4 and unable to discontinue treatment during the duration of the study.

### 9.3.3 Removal of Subjects from Therapy or Study

All subjects are free to withdraw from study participation at any time, for any reason, and without prejudice to their further medical care. In addition, the Investigator may terminate a subject from the study at any time. However, subjects who are removed from pegloticase therapy should remain on study barring withdrawal of consent for study participation.

### 9.3.3.1 Removal of Subjects from Pegloticase Therapy

In addition to completion of therapy through Week 52, the reason for discontinuation from the therapy should be recorded on the eCRF using 1 of the following categories:

- Lack of Efficacy. (i.e., sUA level >6 mg/dL at 2 consecutive study visits beginning with the Week 2 Visit).
- Adverse Event. The subject experiences an AE that imposes an unacceptable risk to the subject's health (e.g., anaphylactic reaction), or the subject is unwilling to continue therapy because of an AE. Subjects who discontinue due to an AE should be followed until resolution or stabilization of the AE, or an adequate explanation for the event is obtained.
- The Investigator has determined that pegloticase administration poses an unacceptable risk to the subject (specify reason).
- Subject refusal of additional therapy (specify reason).
- Study Terminated by Sponsor. The Sponsor, IRB, or regulatory agency terminates the study
- Pregnancy
- Death

### 9.3.3.1.1 Study considerations for subjects ending pegloticase infusions prior to 52 weeks

 Methotrexate, along with folic acid, will be discontinued at the time of cessation of pegloticase infusions prior to Week 52.

Protocol: HZNP-KRY-201

KRYSTEXXA IND: 010122

Version 3.0, Adminstrative Change 1

 All subjects will complete the End of Pegloticase Infusions Visit and will remain on study through week 52 regardless of whether they stop infusions due to sUA stopping rules or other reason (e.g. withdrawal of consent for pegloticase infusions).

- Subjects are encouraged to continue to participate in all visits through the end of the study. Subjects are especially encouraged to complete study visits at the study site during key efficacy and safety collections at Weeks 10, 12, 14, 20, 22, 24, 32, 34, 36, 48, 50 and 52, so that sUA labs and other key assessments can be completed. Subjects who have stopped infusions, may complete the other study visits in person or via telephone to collect AEs, conmeds and gout flare information.
- Activities related to pre/post infusion monitoring or medication dispensation will not be completed once a subject has stopped pegloticase infusions. These activities include:
  - o MTX compliance/reconciliation
  - Infusion reaction prophylaxis
  - IR prophylaxis compliance
  - Folic acid compliance
  - Pegloticase infusion
  - Pegloticase PK sampling
  - Pre-infusion MTX Polyglutamate sampling
  - o MTX drug/dispensation related items

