#### Dose Regimen/Route of Administration:

#### MTX:

During the MTX Run-in Period, which begins 4 weeks prior to the first dose of pegloticase, subjects will take oral MTX at a dose of 15 mg weekly.

Subjects will be instructed to take MTX weekly on the same day each week (if dosing more frequently than once in a day (ie. BID, TID), the total MTX dose should be taken within 24 hours, preferably the same calendar day) and record the date and time of each dose in the dosing calendar.

During the MTX Run-in Period, if a dose is missed, it should be taken as soon as it is remembered. If it is within 48 hours of the next scheduled dose, the subject will be instructed to skip the missed dose and resume at the next regularly scheduled time; thus, subjects will be instructed not to double a dose to make up for a missed dose if within 48 hours of the next dose. Investigators may choose to have subjects take the weekly dose divided over the day (ie. BID, TID). The total MTX dose should be taken within 24 hours, preferably the same calendar day each week, with the date and time of each MTX dose recorded in the dosing calendar.

During the Pegloticase + IMM Period, MTX should be taken 1 to 3 days prior to the pegloticase infusion and one additional weekly dose after the last infusion (at Week 51) for subjects who have not stopped pegloticase due to sUA stopping rules. If a subject is not able to take the MTX 1 to 3 days prior to the pegloticase infusion, MTX must be taken ≥60 minutes prior to the pegloticase infusion.

During the Pegloticase + IMM Period, if a subject becomes unable to tolerate the MTX the dosage may be decreased

Subjects will also take folic acid 1 mg orally every day beginning at Week -4 (the start of MTX) until prior to the Week 52 Visit.

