#### **9.4.1.1** Folic Acid

Subjects will take folic acid 1 mg orally every day beginning at Week -4 (the start of MTX) until prior to the Week 52/End of Study/Early Termination Visit.

If the subject discontinues pegloticase due to the stopping rules or other reason, MTX and folic acid should also be discontinued.

Prescriptions are to be filled at a local pharmacy, as needed. At study visits, the subject will be asked a Yes/No question whether folic acid was taken per protocol.

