#### 9.4.6.3.1.2 Dose and Administration

### **Methotrexate**

During the MTX Run-in Period, which begins 4 weeks prior to the first dose of pegloticase, subjects will take oral MTX at a dose of 15 mg weekly. Subjects will be instructed to take MTX once weekly on the same day each week (if dosing more frequently than once in the day (i.e. BID, TID), the total MTX dose should be taken within the same calendar day) and record the date and time of each dose on each calendar day of MTX administration.

During the MTX Run-in Period, if a dose is missed, it should be taken as soon as it is remembered. If it is within 48 hours of the next scheduled dose, the subject will be instructed to skip the missed dose and resume at the next regularly scheduled time; thus, subjects will be instructed not to double a dose to make up for a missed dose if within 48 hours of the next dose. If a dose is missed, or if infusion schedules are adjusted and MTX dose must be moved from the regular day, it is recommended that the doses are at least 5 days apart if possible, however it is safe for MTX doses to be administered with a minimum of 3 days apart.

During the Pegloticase + IMM Period, subjects will be instructed to take MTX 1 to 3 days prior to the dose of pegloticase; however, if a subject does not do so, MTX must be taken ≥60 minutes prior to pegloticase infusion. Subjects will dose Methotrexate weekly until one week after the last infusion.

If a subject becomes unable to tolerate the prescribed dosage of MTX after Day 1 during the Pegloticase + IMM Period, the dosage may be decreased (see Section 9.4.6.3.2.2).

Refer to Section 9.4.11 for contraception requirements.

Subjects will take folic acid 1 mg orally every day beginning at Week -4 (the start of MTX) until prior to the Week 52 Visit or the last infusion visit. Folic acid will be supplied by a local pharmacy.

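### The protocol's sections conflict on whether a subject who stops pegloticase early takes one more weekly MTX dose, and on when folic acid then ends

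*Protocol*

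**What the plan says.** Three sets of statements cover the end of MTX.

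- **Stop with pegloticase.** Section 9.3.3.1.1, which deals only with subjects ending infusions early, says "Methotrexate, along with folic acid, will be discontinued at the time of cessation of pegloticase infusions prior to Week 52". Section 9.4.1.1 agrees: "If the subject discontinues pegloticase due to the stopping rules or other reason, MTX and folic acid should also be discontinued".
- **One further dose, with one exemption.** Section 9.1 gives "one additional weekly dose after the last infusion for subjects who have not stopped pegloticase due to sUA stopping rules", and the synopsis says the same under Study Design. The synopsis dosing text for MTX adds a date: "one additional weekly dose after the last infusion (at Week 51) for subjects who have not stopped pegloticase due to sUA stopping rules".
- **One further week, with no exemption.** Section 9.4.6.3.1.2 says "Subjects will dose Methotrexate weekly until one week after the last infusion".

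For folic acid, the general statement in Section 9.4.1.1 is "until prior to the Week 52/End of Study/Early Termination Visit", followed by the early-stop sentence quoted above. Section 9.4.6.3.1.2 has "until prior to the Week 52 Visit or the last infusion visit".

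Section 9.3.3.1 lists adverse event as its own reason for ending pegloticase ("Adverse Event. The subject experiences an AE that imposes an unacceptable risk to the subject's health"), separate from lack of efficacy, which is the sUA rule. Subject refusal is another separate category.

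**The concern.** The exemption in Section 9.1 and the synopsis covers only sUA-rule stoppers. Read as written, a subject taken off pegloticase for a reaction, or who refuses more infusions, is directed to take another weekly MTX dose, while Sections 9.3.3.1.1 and 9.4.1.1 direct that MTX stop. A site that works from the dosing section, 9.4.6.3.1.2, finds no exemption and no pointer to Section 9.3.3.1.1. No section says which prevails.

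At stake is consistent dosing of subjects removed from treatment, sometimes for safety reasons, in a study of about 12 to 16 subjects at about 8 centers. The date of the last MTX dose also feeds the treatment-emergent window in Section 9.6.7, the 30-day contact in Section 9.5.6.5 and the partner-pregnancy inquiry in Section 9.5.6.6.

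**Working it through.** The plan gives no figure to reproduce here. The check sets the sections side by side and then counts days.

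**1. Instructions for the last MTX dose in early stoppers**

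| Section | Stops for AE or refusal | Stops by sUA rule |
|---|---|---|
| 9.3.3.1.1 and 9.4.1.1 | no further dose | no further dose |
| 9.1 and Synopsis, Study Design | one further dose | exempt from the further dose |
| Synopsis, MTX dosing | one further dose by its exemption, but dated Week 51 | exempt from the further dose |
| 9.4.6.3.1.2 | one further dose | one further dose |

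Each column holds two incompatible outcomes: no further dose, or one. The sections that conflict differ between the columns.

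**2. Folic acid**

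Sections 9.3.3.1.1 and 9.4.1.1 end folic acid with pegloticase, and the alternative in Section 9.4.6.3.1.2 can end it at the last infusion visit. If one of these is combined with the MTX wording of Section 9.1, the synopsis Study Design text or Section 9.4.6.3.1.2, the remaining MTX dose falls after folic acid has ended.

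**3. Effect on the safety windows**

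Inputs:
- Day 0 is the last infusion, taken as the time of cessation.
- MTX is taken 1 to 3 days before an infusion, or at least 60 minutes before it (Section 9.1). The last pre-infusion dose is therefore on day −k, with k = 0, 1, 2 or 3.
- The window ends 30 days after the later of the last pegloticase and last MTX dose (Section 9.6.7).

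If MTX stops with pegloticase: end = max(0, −k) + 30 = day 30 for every k.

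If one further weekly dose is taken, the last MTX is on day 7 − k and end = (7 − k) + 30:
- k = 0: day 37, a shift of 7 days
- k = 1: day 36, a shift of 6 days
- k = 2: day 35, a shift of 5 days
- k = 3: day 34, a shift of 4 days

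A 30-day contact counted from the last MTX dose alone moves from day 30 − k to day 37 − k, that is, from day 27 to 30 to day 34 to 37.

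**4. Sensitivity to how cessation is dated**

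If cessation is dated at the next visit (assumed day 14) and weekly MTX continued until then, the last MTX is on day 14 − k and the window ends on day 44 − k, that is, day 41 to 44.

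**The case against.** The strongest reply is that the specific text governs the general. The two statements written for early stopping agree with each other and are unconditional. Section 9.3.3.1.1 also ends MTX dispensing once infusions stop. The synopsis dates the extra dose at Week 51, and the Schedule of Assessments and the Week 50 visit note tie it to the Week 50 infusion. On this view the last infusion means the 26th, and the extra dose was meant for completers.

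That is a plausible account of intent, but the protocol does not state it. Section 9.1, the synopsis Study Design text and Section 9.4.6.3.1.2 carry no Week 51 limit. The exemption for sUA-rule stoppers also suggests that early stoppers were in mind, since a dose reserved for completers would need no such exemption.

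Several parts of the reply do stand:
- A reader might infer three different end points for one subject. Any given stopper faces two.
- A reader might take the Week 50 note, or the general Week 52 sentence in Section 9.4.1.1, as a further folic acid conflict. The note concerns completers, and Section 9.4.1.1 carries its own early-stop exception. The alternative in Section 9.4.6.3.1.2 can likewise be read as completers versus early stoppers. The folic acid gap therefore arises only when sections are combined as in step 2.
- A reader might infer that the same event would be treatment-emergent at one site and not at another. Section 9.6.7 applies one rule everywhere, based on the actual last dose, and Section 9.4.10 provides for recording dose dates. A longer window after a later dose reflects real exposure.
- A reader might size the problem from the 26% infusion-reaction rate in Section 7.1. That is the rate of any infusion reaction, not of stopping, and Section 9.4.6.3.2 allows infusions to continue after some reactions.
- The MTX guidance in Section 9.4.6.3.2.2 would itself call for a temporary stop after some serious reactions, whichever end-date sentence a site reads.

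**Conclusion.** The contradiction stands. Subjects who stop for an adverse event or refusal get opposite instructions from Sections 9.3.3.1.1 and 9.4.1.1 on one side and Section 9.1, the synopsis Study Design text and Section 9.4.6.3.1.2 on the other. Subjects stopped by the sUA rule get opposite instructions from Section 9.4.6.3.1.2 and the rest.

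The size is modest: at most one further weekly MTX dose per early stopper, possibly after folic acid has ended, a treatment-emergent window that ends 4 to 7 days later, and MTX-dated safety contacts up to 7 days later. These counts assume that cessation is dated at the last infusion and that MTX was taken 0 to 3 days before it. The number of subjects affected cannot be derived, because the protocol gives no rate of early stopping by reason.

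The documents do not support a reading that safety data are lost or efficacy is biased. Section 9.5.4.1.2 collects adverse events to the 6-month follow-up, Section 9.6.7 summarises those beyond the 30-day window, and the primary endpoint does not depend on the window. The reason to act is that dosing of a subject taken off pegloticase should not depend on which section a site opens.

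**What to change.** Reconcile the synopsis (Study Design and MTX dosing text) and Sections 9.1, 9.3.3.1.1, 9.4.1.1 and 9.4.6.3.1.2 into one statement. It should give the last MTX dose and the last folic acid dose for three groups: completers, sUA-rule stoppers, and stoppers for any other reason. It should also say from which day cessation is counted. Replace the other statements with a cross-reference to it. Which rule applies in each group is for the sponsor to decide.

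The cost is amendment wording only, with no added visits, samples or analyses.
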